#### 2-5 Year Annual Follow-up Visit

All patients will undergo the following assessments within the 2-5 Year annual follow-up period:

- Pertinent physical examination [include blood pressure, weight and all major systems findings]
- Adverse events
- Current cardiac medications and all medications given for cardiovascular effect
- NYHA functional classification
- CSS Angina Classification
- Comprehensive TTE. If not adequate, a TEE will be performed

For patients with abnormal findings related to valve integrity and position and patients with adverse events related to worsening valve function, fluoroscopic imaging of the implanted valve will be completed.

#### Missed Visits

Every patient should be encouraged to remain in the study until they have completed the protocol-required follow-up period. If the patient discontinues prematurely from the study, the reason for discontinuation must be documented on the appropriate case report form (CRF). Possible reasons for premature discontinuation may include, but are not limited to the following:

- Withdrawal of consent: Patient decides to withdraw from the study. If a subject withdraws from the clinical investigation, the reason(s) should be recorded. If such withdrawal is due to problems related to the investigational device safety or performance, the investigator shall ask for the subject's permission to follow his/her status/condition outside the investigation.
- Lost to follow-up: All patients should be encouraged to return to the clinic for evaluation during follow-up (excluding 6 Month telephone visit). If a patient is unable to return to the clinic, 3 separate telephone calls should be made to attempt to bring the patient back into the clinic or obtain safety information. All attempts should be documented in the source documents. If the patient does not respond to the 3 telephone calls then the Investigator should send a certified letter to the subject.

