#### 7.1.6 Safety and Effectiveness evaluation methods

##### Primary Endpoint

The primary endpoint is all-cause mortality at 30 days post-index procedure.

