### 8.3 Expected expulsion rate

The Chinese regulatory requirements determine 50 patients should meet the primary endpoint. If a minimum of 50 patients complete 30 Day visit and upto 60 patients have the procedure, the expected drop-out rate is <17%.

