### 8.4 Statistical method for all data, together with deficient, unused or fault data (including drop out and withdrawal) and method for treating unreasonable data

The primary and secondary endpoints will be reported based on the AT Population. Descriptive and summary statistical analysis will be performed on all endpoints. Patient listings for adverse events, deaths, and reinterventions will include all enrolled patients.

All clinically relevant baseline and follow-up variables will be tabulated. Descriptive statistics for continuous variables include mean, standard deviation, sample size, median, minimum, and maximum) and frequency tables or proportions for discrete variables.

Kaplan Meier estimates will be performed at the pre-specified follow-up times to project the estimates for time-related endpoints such as the 30-day mortality rate, the primary endpoint; the standard error and confidence limits will be computed using Greenwood's algorithm. Based on 50 patients as point estimate and length of estimate on the primary endpoint, the 30 days death rate and 95% confidence interval will be summarized.

Echocardiographic data will be analyzed by an Echo core laboratory with respect to the degree of total aortic valve regurgitation (TVR) and paravalvular aortic valve regurgitation (PAR) according to the VARC-2 definitions [29].

These data and other categorical data (e.g., NYHA class) will also be presented as shift from baseline for each of the pre-specified follow-up periods.

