## 13. Provisions on adverse event and device defect report

### 13.1 Adverse events

Adverse events may be volunteered by patients, elicited from questioning by Investigator or delegated study personnel, or collected via observation by the Investigator. In addition, patients will be instructed to contact the investigator, and/or study coordinator if any significant adverse events (e.g., expanded safety composite events) occur between study evaluation visits.

All adverse events are reported from the start of the procedure, which is defined as when anesthesia is first administered, and are reported until subject participation has ended (i.e. completion of the study or withdrawal of consent). Adverse events must be reviewed at every follow-up visit until resolution, AE has stabilized (according to Investigator), or the study has been completed. Should the adverse event be ongoing at time of study completion, the database should be updated to reflect status.

Reporting guidelines for adverse events:

- Record the number of units of blood needed for any transfusion associated with any overt bleeding event

- Failure of a percutaneous closure device shall be reported as an access site vascular closure device complication
- Vascular complications shall be designated as access or non-access related;

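### The plan does not secure day-30 vital status for treated patients who withdraw consent before day 30, whatever their reason

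*Combined protocol and SAP*

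**What the plan says.** Section 7.1.6 defines the endpoint: "The primary endpoint is all-cause mortality at 30 days post-index procedure". Section 8.4 sets the population: "The primary and secondary endpoints will be reported based on the AT Population". Under section 8.6 that population is every enrolled, non-roll-in patient in whom an investigational device was inserted. Section 8.4 estimates the 30-day death rate by Kaplan-Meier with Greenwood limits and a 95% confidence interval.

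The Missed Visits text in section 7.1.5.2 sets two duties when consent is withdrawn. The first applies to everyone: "If a subject withdraws from the clinical investigation, the reason(s) should be recorded". The second is conditional: "If such withdrawal is due to problems related to the investigational device safety or performance, the investigator shall ask for the subject's permission". What is sought is "permission to follow his/her status/condition outside the investigation".

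Section 13.1 says that adverse events "are reported until subject participation has ended (i.e. completion of the study or withdrawal of consent"), with no distinction by reason. Section 8.3 says that "the expected drop-out rate is <17"%, from 50 patients completing the 30-day visit out of up to 60 treated. Section 9.2 promises to keep missing data to a minimum but gives no analysis rule for unknown vital status.

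**The concern.** For death from any cause, the reason for leaving has no bearing on whether vital status is needed. Yet the only request for continued follow-up depends on that reason, and even then the information is gathered outside the trial. Read with section 13.1, no provision brings day-30 vital status into the trial data for a patient who withdraws consent before day 30.

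Such a patient would presumably be censored on leaving. Kaplan-Meier then treats that patient's later risk as equal to that of the patients who remain. If those who leave early after the procedure tend to be sicker, 30-day mortality is understated. This is a single-arm study of 50 to 60 patients, so one or two unknown outcomes move the estimate visibly, and there is no control arm in which similar losses might offset.

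**Working it through.** **1. The plan's own figure.** 1 - 50/60 = 16.7%, which agrees with the figure below 17% in section 8.3. It means at most 10 of 60 patients not completing the 30-day visit for any reason, including death, a missed visit or loss to follow-up. It is a ceiling on all non-completion, not a forecast of withdrawals.

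**2. What the text provides in each situation.**

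| Situation | Required step | Day-30 vital status in the trial data |
|---|---|---|
| Cannot be reached or cannot return | Three calls and a letter; contact with physicians, family or an intermediary | Actively sought |
| Withdraws consent before day 30, device-related reason | Reason recorded; permission sought for follow-up outside the trial | Not provided for |
| Withdraws consent before day 30, any other reason | Reason recorded | Not provided for |
| Withdraws consent after day 30 | Reason recorded; permission sought if device-related | Already known (alive at day 30) |

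The gap is in the second and third rows.

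**3. Possible size.** The documents give neither an expected death rate nor a number of early withdrawals, so the following inputs are assumptions: N = 60 treated patients, d = 2 known deaths by day 30, and m patients who withdraw before day 30 with unknown status.

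- Kaplan-Meier estimate: between d/N (all m censored after the last death) and d/(N - m) (all m censored before the first death).
- Full-information rate: between d/N (none of the m died) and (d + m)/N (all died).
- Value of one unobserved death: 1/60 = 1.7 percentage points.

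| m | Kaplan-Meier reports | If one of the m died | If all m died |
|---|---|---|---|
| 1 | 2/60 to 2/59 = 3.3-3.4% | 3/60 = 5.0% | 3/60 = 5.0% |
| 3 | 2/60 to 2/57 = 3.3-3.5% | 3/60 = 5.0% | 5/60 = 8.3% |
| 5 | 2/60 to 2/55 = 3.3-3.6% | 3/60 = 5.0% | 7/60 = 11.7% |

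The ceiling of 10 would already include the 2 assumed deaths, so at most 8 of the 60 could be of unknown status within the plan's own allowance.

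**4. Against sampling error.** The exact 95% interval is 0.4-11.5% for 2/60 and 2.8-18.4% for 5/60. The shift from 3.3% to 8.3% lies inside the first interval. It is a possible bias rather than sampling error, however, and the Greenwood limits do not allow for it.

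**The case against.** Several points on the other side stand.

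- A reader might infer that 30-day vital status is lost for every withdrawal that is not device-related. The documents do not support that. Patients who withdraw after day 30 are known to have been alive at day 30, and the text forbids no investigator from asking an earlier one. Status is not secured, rather than certainly lost.
- A reader might also infer that the endpoint is selectively incomplete by reason for withdrawal. That is not shown. Follow-up of device-related withdrawals is itself outside the trial, and adverse event reporting stops for everyone, so neither group's outcome is routed into the trial data. The gap is the same for both.
- It is tempting to take 10/60 = 16.7% as the number of withdrawals with unknown status. It is a ceiling on all non-completion.
- Some of the sicker patients, such as those too unwell to return, need not withdraw consent. They may fall under the tracing steps in Follow-Up Visits and Missed Visits, which seek safety information.
- There is no hypothesis test or performance goal, so no pass/fail decision turns on one outcome. All the time-specified endpoints are at 30 days or earlier; later withdrawals affect only later Kaplan-Meier time points.
- The consent form is not in the supplied text, and section 8.5 defers further statistical detail to a SAP that is not supplied separately. Either may already deal with part of this.

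These points narrow the concern without removing it. The tracing steps do not cover a patient who withdraws consent, recording the reason does not supply the outcome, and a SAP cannot recover data that nobody asked for.

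**Conclusion.** The concern holds in a limited form. Followed as written, the plan does not secure day-30 vital status for As Treated patients who withdraw consent before day 30, for any reason, and it states no handling for status that remains unknown. The effect depends on how many patients withdraw early, which the documents do not say. In the assumed case of 2 known deaths and 3 early withdrawals among 60, a reported 3.3-3.5% would stand against 5.0-8.3% if 1 to 3 of the three died.

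This rests on early withdrawals being censored, which section 8.4 implies but does not state, and on a denominator of 60. The As Treated population can be somewhat larger, because the cap of 60 counts only patients who leave the procedure room with the valve; one death would then be worth slightly less than 1.7 points. Closing the gap is a cheap improvement.

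**What to change.** Amend the Missed Visits text so that every patient who withdraws, whatever the reason, is asked for permission to collect vital status by telephone, from the treating physician or from records. It should be collected at day 30 if the patient leaves earlier, and at the later scheduled time points. The additional request about condition after device-related withdrawals can stay.

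State that this vital status is entered in the eCRF and used in the As Treated mortality analysis, and that the number who refuse is reported. In section 8.4 or the SAP, add a best-case/worst-case analysis for any day-30 status still unknown: d/N and (d + m)/N beside the Kaplan-Meier estimate. Align section 13.1 so that the end of adverse event reporting does not appear to bar the permitted vital status check. Align the consent form if it does not already allow this.

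The cost is a few sentences and a few calls or record checks. Some patients will refuse; their choice is respected and their number reported.

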#### Standard of Care

All enrolled patients will receive the standard of care during the clinical trial as well as following

the conclusion of their participation. Any patients with symptoms of valve failure at any time throughout the study duration should undergo standard diagnostic imaging (e.g. (TTE)) to assess valve function. Each patient will be provided with an implant card. This implant card can be carried by the patient to be shown to any clinician to inform a treating physician of the implanted SAPIEN 3 THV. Subjects that are enrolled, but not treated with the SAPIEN 3 THV will likely be screened for alternative treatments (when available) or continue with the care they have been receiving to date.

#### 7.1.6 Safety and Effectiveness evaluation methods

##### Primary Endpoint

The primary endpoint is all-cause mortality at 30 days post-index procedure.

##### Secondary Endpoints

##### Safety Endpoints

- Cardiovascular and non-cardiovascular mortality at 72 hours (peri-procedural) and 30 days
- Stroke at 30 days
- TIA at 30 days
- All-cause mortality & disabling stroke at 30 days
- Vascular complications (major) at 30 days
- Bleeding complications (life threatening or disabling, and major) at 30 days
- Myocardial infarction at 30 days
- Acute kidney injury at 30 days (stages II and III)
- Coronary obstruction requiring intervention at 30 days
- Arrhythmia and conduction disturbance at 30 days
- Permanent pacemaker implantation at 30 days
- Valve-related dysfunction requiring repeat procedure (BAV, TAVI or SAVR) at 30 days
- Mitral valve apparatus damage or dysfunction at 30 days
- Unplanned use of cardiopulmonary bypass (CPB) during TAVI implant procedure
- Pericardial tamponade at 30 days
- Endocarditis at 30 days
- Valve thrombosis at 30 days
- Valve malposition (migration, embolization, and ectopic deployment) at 30 days
- Ventricular septal perforation at 30 days

##### Device and Procedure Success Composite

- Absence of procedural mortality AND
- Correct positioning of a single prosthetic heart valve into the proper anatomic location AND
- Intended performance of the prosthetic heart valve (no prosthesis-patient mismatch and mean aortic valve gradient <20mmHg or peak velocity <3m/s, AND no moderate or severe prosthetic valve regurgitation) at 30 Days

##### Efficacy

- New York Heart Association (NYHA) Classification at 30 days
- Hemodynamic valve performance evaluation by echocardiography for aortic valve stenosis and aortic valve regurgitation (paravalvular & central) at 30 Days as determined by Echo core lab

[figure not shown]
## Quality of Life

- KCCQ at 30 days

### 7.2 Test process

#### 7.2.1 Test flowchart

Figure 2. Trial Process Diagram

#### 7.2.2 Specification for use of devices

## Study Device

The SAPIEN 3 and its delivery components will have a unique product identifier. This information will be recorded in the study subject's medical file. The Instructions for Use for the SAPIEN 3 THV System are provided with the device.

## Storage & Labeling

The SAPIEN 3 THV System is to be stored as specified on the unit labels. All investigational stock will be stored in a secure and controlled area.

## Device Accountability

The Investigator shall maintain accurate records of the receipt and disposition of the investigational devices. A device disposition log supplied by Edwards will be used to record device receipt, uses, discards, or returns. Device disposition will be verified by the Sponsor periodically throughout the study. All unused devices shall return to Edwards, along with the completed device disposition log at completion of the enrolment period. The Investigator's copy of the device disposition log must document the devices used in study subjects as well as unused devices that are returned to Edwards. Use of the SAPIEN 3 THV System is prohibited outside of this protocol.

## 7.3 Monitoring Plan

Edwards Lifesciences will contract with a Contract Research Organization (CRO) to provide a Clinical Research Associate(s) (CRA) to monitor the study sites to ensure that all investigators are in compliance with the protocol and the Investigator's Agreement, and that all study subjects have been properly consented with the current version of the informed consent document. Edwards Lifesciences will evaluate circumstances where an investigator deviates from the clinical protocol and will retain the right to remove either the investigator or the investigational site from the study.

Routine on-site monitoring visits shall include verification of the following:

- Compliance with the protocol, any subsequent amendment(s), GCP and maintenance of regulatory and EC requirements. Deviations shall be discussed with the Investigator(s) or delegated personnel, documented and reported
- Only authorized and delegated individuals are participating in the study
- The SAPIEN 3 THV System is being used according to the protocol and IFU
- Study Site resources, equipment and study personnel, remain adequate throughout the duration of the study
- Patient Informed Consent is completed in accordance to the protocol and regulations
- Only Patient Informed Consents Forms approved by the EC are used appropriately
- Source documents and other clinical records are accurate, complete up to date, stored and maintained properly
- CRFs and queries are complete, recorded in a timely manner, and consistent with source documents
- All adverse events and device deficiencies are reported to Edwards without unjustified delay
- All serious adverse events and deviations are reported to the EC, if required

- All other required reports, notifications, applications, submissions and correspondence are maintained in the investigator's files and are accurate, complete, timely, legible, dated and identify the clinical investigation
- Current laboratory normal values, laboratory certifications, accreditations, or other validations are present in the investigator's file
- Subject withdrawal has been documented; the monitor shall discuss this with the principal investigator or his/her authorized designee
- Subject non-compliance with the requirements stated in the informed consent has been documented; the monitor shall discuss this with the principal investigator or his/her authorized designee
- Suitability of the attempts to contact lost to follow-up patients and any intermediaries
- The principal investigator and investigation site team are informed and knowledgeable of all relevant document updates concerning the clinical investigation
- Any corrective and preventive actions, as needed, have been implemented and are effective.

Monitors shall be appropriately qualified per the following requirements:

- Qualified in the field of the applicable regulations and GCP through training and experience as well as scientific or clinical knowledge;
- Knowledgeable on the use of the investigational device(s) and relevant requirements, protocol and informed consent process;
- All monitoring activities shall be documented in a written report. The frequency of monitoring visits will depend on enrollment and center compliance, but each center will at least be visited once per year. Further details are laid out in the monitoring plan.

Edwards Lifesciences will review significant new information, including unanticipated adverse events and ensure that such information is provided to the study investigators and to all reviewing ECs and regulatory agencies as necessary. Efforts will be made to ensure that data collection compliance is monitored and communicated to the Investigators in a timely manner throughout the trial.

## **8. Statistical considerations**

### **8.1 Statistical design, method, and analysis procedures**

The clinical study is a single-arm prospective study intended to demonstrate the safety and performance of the SAPIEN 3 THV in the Chinese population.

### **8.2 Sample Size**

The sample size of 50-60 patients is determined per Chinese regulatory requirements and agreement for a regional study of a medical device already approved in other regions based on a well-designed prospective study.

#### **8.2.1.1 Minimum and maximum number of subjects for each clinical trial institution and reasons**

To ensure that a minimum of 50 patients are implanted with the SAPIEN 3 THV and complete the 30 Day follow-up for Primary Endpoint, up to 60 patients will be enrolled and implanted with

SAPIEN 3 THV. Each site may not contribute more than 25 implanted patients to the study population.

### 8.3 Expected expulsion rate

The Chinese regulatory requirements determine 50 patients should meet the primary endpoint. If a minimum of 50 patients complete 30 Day visit and upto 60 patients have the procedure, the expected drop-out rate is <17%.

### 8.4 Statistical method for all data, together with deficient, unused or fault data (including drop out and withdrawal) and method for treating unreasonable data

The primary and secondary endpoints will be reported based on the AT Population. Descriptive and summary statistical analysis will be performed on all endpoints. Patient listings for adverse events, deaths, and reinterventions will include all enrolled patients.

All clinically relevant baseline and follow-up variables will be tabulated. Descriptive statistics for continuous variables include mean, standard deviation, sample size, median, minimum, and maximum) and frequency tables or proportions for discrete variables.

Kaplan Meier estimates will be performed at the pre-specified follow-up times to project the estimates for time-related endpoints such as the 30-day mortality rate, the primary endpoint; the standard error and confidence limits will be computed using Greenwood's algorithm. Based on 50 patients as point estimate and length of estimate on the primary endpoint, the 30 days death rate and 95% confidence interval will be summarized.

Echocardiographic data will be analyzed by an Echo core laboratory with respect to the degree of total aortic valve regurgitation (TVR) and paravalvular aortic valve regurgitation (PAR) according to the VARC-2 definitions [29].

These data and other categorical data (e.g., NYHA class) will also be presented as shift from baseline for each of the pre-specified follow-up periods.

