#### Follow-Up Visits

The determination of the study endpoints will require rigorous clinical follow-up and quality data collection. The Investigator or delegated study personnel will ensure the patient is scheduled for follow-up visits according to Table 5.

Table 4. Follow-up Visit Windows

Follow-Up Visit	Visit Window (days following Procedure)
30 Day	30 days, +14 days
6 Month	180 days +/-30 days
1 Year	365 days +/-60 days
2 Year	730 days +/-60 days
3 Year	1095 days +/-60 days
4 Year	1460 days +/-60 days
5 Year	1825 days +/-60 days

The importance of attending the 30 Day follow-up visit should be discussed with the patient. Planned absences should be recorded to facilitate continued ability to contact a study patient during the course of the study. If a patient cannot be reached for a follow-up visit, the investigator will document on the follow-up data form, the efforts undertaken to contact the patient, referring physicians, including internists as well as cardiologists, family members, or other alternate contacts noted in the study patient's records. These efforts should include 3 attempts of telephone contacts at separate dates and times, and a registered letter. If a patient can no longer be located, the investigator must contact an intermediary (e.g. patient's private physician) without delay.

Patients for whom the study procedure was begun but do not receive and retain the study valve will be followed up until the 30-day assessment or resolution of any AE for safety purposes. Patients with an ongoing AE at the 30 Day visit should have AEs reassessed at 30 day window closure (day 44). These patients should then be exited from the study. In the event that the patient's implanted

valve is explanted, the patient needs to be followed up until resolution of any AE for safety purposes. These patients should then be exited from the study.

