### 30-Day Visit

All patients will undergo the following assessments within the 30-Day follow-up period +14 days):

- Pertinent physical examination [include blood pressure, weight and all major systems findings]
- Adverse events
- Current cardiac medications and all medications given for cardiovascular effect
- NYHA functional classification
- CSS Angina Classification
- Neurological assessments
  - NIHSS
  - mRS
- 6 Minute Walk Test (6MWT)
- KCCQ
- Clinical Laboratory Test
  - Blood count (hemoglobin, hematocrit, platelet count, white blood cells)
  - Creatinine
  - CK/CK-MB and/or troponins
  - Albumin
- 12-Lead ECG
- Comprehensive TTE. If not adequate, a TEE will be performed

For patients with abnormal findings related to valve integrity and position and patients with adverse events related to worsening valve function, fluoroscopic imaging of the implanted valve will be completed.

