#### Analysis Sets

- *As Treated (AT) Population*: all patients that were enrolled in the trial for whom the SAPIEN 3 valve implant procedure was begun, defined as the time in which the first Edwards' investigational device is inserted into the patient.

- *Valve Implant (VI) Population:* all AT patient who received and retained the SAPIEN 3 valve upon leaving the procedure room

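### Section 8.4 puts 30-day valve haemodynamics on the As Treated set, so echo values from patients without a SAPIEN 3 valve can enter the device's performance tables; the Valve Implant set fits better

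*Combined protocol and SAP*

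**What the plan says.** Section 8.4 sets one rule for all endpoints: "The primary and secondary endpoints will be reported based on the AT Population". It makes no exception for echocardiography.

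The secondary endpoints in sections 3.2 and 7.1.6 include, under Efficacy, "Hemodynamic valve performance evaluation by echocardiography for aortic valve stenosis and aortic valve regurgitation" at 30 days, read by the core laboratory. Section 8.4 also plans shift-from-baseline tables for the echo data.

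Section 8.6 (Analysis Sets) defines two populations:

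- AT: "all patients that were enrolled in the trial for whom the SAPIEN 3 valve implant procedure was begun", with the start "defined as the time in which the first Edwards' investigational device is inserted into the patient". Receiving a valve is not required.
- VI: "all AT patient who received and retained the SAPIEN 3 valve upon leaving the procedure room".

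No analysis is assigned to VI in the available text. Section 7.1.5.1 uses the same idea, without naming the set, only to count patients toward the 60 implants.

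Two rules govern whether a patient without the valve has a 30-day echo. Section 7.1.5.2 (Follow-Up Visits) says: "Patients for whom the study procedure was begun but do not receive and retain the study valve will be followed up until the 30-day assessment". It gives resolution of any adverse event as the alternative end point and safety as the purpose. The 30-Day Visit subsection says "All patients will undergo the following assessments within the 30-Day follow-up period", and its list includes "Comprehensive TTE. If not adequate, a TEE will be performed".

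**The concern.** A haemodynamic summary of a prosthesis should describe that prosthesis. Under the stated rule, a patient whose implant was abandoned, or who left the room with a different valve, belongs to the denominator of the SAPIEN 3 gradient and regurgitation tables. The shift tables inherit the problem.

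The distortion has no fixed direction. A native stenotic valve raises the mean gradient. A surgical prosthesis may leave the gradient unchanged or lower total regurgitation. Paravalvular regurgitation has no meaning for a native valve, so the analyst must either score such a patient as having none or drop the patient under a rule that the plan does not give.

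The study is meant to show safety and performance for a regulatory submission (sections 3.1 and 8.1). With 50 to 60 patients, a few such values would be visible in the tables.

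**Working it through.** **The plan's own figure.** The only derived number in section 8 is the drop-out rate in 8.3: 1 − 50/60 = 16.7%, which agrees with the stated bound of less than 17%. This point does not depend on it.

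**Do the rules allow pooling?**

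1. Section 8.4 assigns every secondary endpoint to AT.
2. 30-day valve haemodynamics is a secondary endpoint.
3. AT requires only device insertion, so AT can be larger than VI.
4. The protocol foresees such patients: Follow-Up Visits has a rule for them, and Standard of Care describes what may follow for enrolled patients not treated with the valve.
5. The 30-Day Visit lists a TTE for all patients. The specific rule for non-implanted patients lets follow-up end at adverse event resolution, so a 30-day echo is possible but not certain.

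Pooling therefore occurs whenever an AT patient outside VI has a 30-day echo. The discharge TTE is also listed for all study patients. It cannot enter the 30-day endpoint, but it could enter a discharge shift table.

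**Size.** The documents give neither the number of such patients (k) nor any expected gradient, so all inputs below are assumptions. A mean gradient above 40 mmHg is one of several alternative ways to meet inclusion criterion 2. Values of 45 or 50 mmHg are therefore compatible with entry but not implied by it.

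*Scenario A: 60 echoes in all, SAPIEN 3 mean 12 mmHg, native mean 50 mmHg, SD 5 within each group, p = k/60.*

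Mean = 12(1 − p) + 50p. SD = √(25 + p(1 − p) × 38²).

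| k | Mean | SD |
|---|---|---|
| 0 | 12.0 | 5.0 |
| 1 | 12 + 38/60 = 12.6 | √(25 + 23.7) = 7.0 |
| 2 | 12 + 76/60 = 13.3 | √(25 + 46.5) = 8.5 |
| 3 | 12 + 114/60 = 13.9 | √(25 + 68.6) = 9.7 |

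*Scenario B: n implanted patients (12 mmHg, SD 5) plus k native valves, all at 45 mmHg. Only implanted patients count toward 60, so AT can exceed 60.*

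Mean m = (12n + 45k)/(n + k). SD = √{[25(n − 1) + n(12 − m)² + k(45 − m)²]/(n + k − 1)}.

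| k | n = 60: mean (SD) | n = 50: mean (SD) |
|---|---|---|
| 1 | 12.5 (6.5) | 12.7 (6.8) |
| 2 | 13.1 (7.7) | 13.3 (8.1) |
| 3 | 13.6 (8.6) | 13.9 (9.1) |

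*Scenario C: as B with n = 60, but the k patients have another prosthesis at 12 mmHg.* The mean stays at 12.0 and the SD moves only from 5.0 to about 4.9 for k = 3. The values still do not describe SAPIEN 3.

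**Categorical tables.** One patient shifts a percentage by 1/61 = 1.6 to 1/50 = 2.0 points.

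**The case against.** Several objections have force.

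- **Detail is deferred.** Section 8.5 leaves further methods to a separate SAP that is not among the documents. A reader might infer that VI is never used. The documents do not support that: they show only that the available text gives it no analysis. An SAP that moved echo to VI would still conflict with the sentence in 8.4.
- **A 30-day echo is not guaranteed.** A reader might infer that every non-implanted patient reaches a 30-day TTE. Follow-Up Visits allows an earlier exit on adverse event resolution and gives safety as the reason for follow-up. Pooling is a consequence that the rules permit, not an established one.
- **The scenario is chosen.** Inclusion criterion 1 requires operable patients, so a failed implant need not leave a stenotic native valve. Scenario C shows that the mean then may not move.
- **Outliers would be seen.** Section 8.4 reports the sample size, median, minimum and maximum beside the mean and SD, so one or two native-valve gradients would probably be noticed.
- **Nothing is tested.** The analyses are descriptive, with no margin or power calculation.

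These points limit the size and certainty of the effect. They do not remove it, because the sentence in 8.4 is an explicit rule and would produce a misattributed summary whenever AT and VI differ among patients with an echo.

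**Conclusion.** The point holds as a low-cost improvement. Section 8.4 assigns prosthesis haemodynamics to a set that can include patients without the prosthesis, and the set that suits the purpose has no stated use in the available text.

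The size rests on an unstated number of patients and on assumed gradients. With 1 to 3 native valves, the mean rises by 0.6 to 1.9 mmHg in scenario A and by 0.5 to 1.9 mmHg in scenario B. The SD rises from 5.0 to between 6.5 and 9.7 across both. If the other valves perform like SAPIEN 3, the mean does not change. If every AT patient leaves with the valve and keeps it as the only aortic prosthesis until the echo, nothing changes.

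A reader might conclude that the haemodynamic endpoint no longer measures the study valve. That is too strong for 1 to 3 patients in about 60: the summary would still be mostly SAPIEN 3, with a modest shift in the mean and a larger inflation of the spread. The primary endpoint and the sample size are unaffected.

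**What to change.** In section 8.4, add an exception to the AT rule:

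- Report echocardiographic haemodynamic performance and its shift tables on the VI population, using echoes taken while the originally implanted SAPIEN 3 valve is in place and is the only prosthesis in the aortic position.
- List separately the explants and valve reinterventions that occurred before the echo. This is needed because VI membership is fixed when the patient leaves the procedure room, so VI alone would still admit a valve replaced before day 30.
- Keep mortality, all safety endpoints and the device and procedure success composite on AT, so that a failed implant counts as a failure.

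The change takes a few sentences, uses a population already defined and needs no new data. It has two costs. The tables carry a second denominator. The haemodynamic results also become conditional on implant success, so they should be shown beside the AT device success rate. If a separate SAP exists, its assignment of analysis sets should be made to agree with 8.4.
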